## 7.1 Assessment of Severity (Intensity)

The following definitions for rating severity (intensity) will be used:

- Mild:** A type of AE that is usually transient and may require only minimal treatment or therapeutic intervention. The event does not generally interfere with usual activities of daily living
- Moderate:** A type of AE that is usually alleviated with specific therapeutic intervention. The event interferes with usual activities of daily living, causing discomfort but the subject is still able to function
- Severe:** The type of AE that interrupts usual activities of daily living, or significantly affects clinical status, or may require intensive therapeutic intervention.

## 7.2 Assessment of Relationship to Study Drug

The Investigator will use his/her clinical judgment to explain each adverse event and determine its relationship, if any, to study drug treatment. Alternative causes, such as natural history of the underlying diseases, concomitant therapy, other risk factors, and the temporal relationship of the event to the study drug will be considered and investigated. The Investigator will also consult the Investigator's Brochure in the determination of his/her assessment. Causality should be assessed using the following categories:

- Not related** The event could readily be explained by factors not involving the study drug and a temporal relationship with the study drug did not exist.
- Possibly Related** There was some temporal relationship between the event and the administration of the study drug and the event was unlikely to be explained by the subject's medical condition or other therapies.
- Probably Related** The temporal relationship between the event and the administration of the study drug was suggestive, and the event was less likely to be explained by the subject's medical condition or other therapies.
- Definitely Related** The event followed a reasonable temporal sequence from administration of the study drug, followed a known or suspected response pattern to the study drug, was confirmed by improvement upon stopping the study drug (dechallenge) and reappeared upon repeated exposure (rechallenge). (NOTE: this was not to be construed as requiring re-exposure of the subject, however, a category of definitely related could only be used when recurrence was observed.).

## 7.3 Serious Adverse Events

An SAE is any untoward medical occurrence that:

- Results in death.

- Is life-threatening. NOTE: The term ‘life threatening’ in the definition of “serious” refers to an event in which the subject was at risk of death at the time of the event; it does not refer to an event which hypothetically might have caused death if it was more severe.
- Results in persistent or significant disability/incapacity.
- Requires in subject hospitalization or prolongation of existing hospitalization. NOTE: Hospitalizations, which are the result of elective or previously scheduled surgery for pre-existing conditions, which have not worsened after entry into the study, should not be classified as SAEs. For example, admission for a previously scheduled ventral hernia repair would not be classified as an SAE; however, complication(s) resulting from a hospitalization for an elective or previously scheduled surgery that meet(s) serious criteria must be reported as SAE(s).
- Is a congenital anomaly/birth defect.
- Is an important medical event.

NOTE: Medical or scientific judgment should be exercised in deciding whether reporting is appropriate in other situations, such as important medical events that may not be immediately life threatening or result in death or hospitalization but may jeopardize the subject or may require medical or surgical intervention to prevent one of the other outcomes listed in the above definition. These should also be considered serious. Examples of such events are invasive or malignant cancers, intensive treatment in an emergency room or at home for allergic bronchospasm, blood dyscrasias, or convulsions that do not result in hospitalization, or development of drug dependency or drug abuse.

All SAEs for subjects occurring from the time of informed consent through the LFU visit must be reported to Nabriva Therapeutics AG or their representative within 24 hours of the knowledge of the occurrence (this refers to any AE that meets one or more of the aforementioned serious criteria). Reporting is done by completing the SAE form electronically in the Electronic Data Capture (EDC) system for the study. When the form is completed, PPD Pharmacovigilance (PVG) will be notified electronically and will retrieve the form. If the event meets serious criteria and it is not possible to access the system, site must fax the completed paper SAE report form to PPD PVG within 24 hours of awareness or call the PPD PVG SAE hotline. When the EDC system becomes available, the SAE information must be entered within 24 hours of the system becoming available. PPD PVG personnel are available for SAE reporting on a 24 hour basis. Reports are reviewed during normal business hours. EDC and/or report forms should be completed in as much detail as possible but lack of complete information should not delay the reporting of the SAE.

There may be situations when an SAE has occurred and the Investigator has minimal information to include in the initial report to Nabriva Therapeutics AG, or their representative. However, it is very important that the Investigator always makes an assessment of causality for every event prior to transmission of the SAE report form to Nabriva Therapeutics AG, or their representative. The Investigator may change his/her opinion of causality in light of follow-up information, amending the SAE report form accordingly. The causality assessment is one of the criteria used when determining regulatory reporting requirements.

The Investigator will provide the assessment of causality as per instructions on the SAE form in the subject's eCRF. SAEs that are determined by the Investigator to be related to the study drug must be reported even if more than 30 days after the last administration of study drug.

The sponsor will not routinely unblind the therapy assignment for an individual subject in the event of a serious adverse event. However, unblinding of an individual subject may occur if this information is requested by the Investigator, if the Sponsor determines that the information is necessary to adequately assess safety, or if this information is required for reporting to local regulatory authorities (see Section 5.9).

All serious adverse events and suspected unexpected serious adverse events (SUSARs) will be reported by the sponsor to the relevant competent authorities in accordance with the European Directive 2001/20/EC, as applicable.

## **7.4 Symptoms of the Disease Under Study**

In this study, clinical signs and symptoms of pneumonia which are assessed daily per protocol (i.e., dyspnea, cough, sputum production, and chest pain) will not be reported as adverse events unless they meet the definition of a serious adverse event.

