### 1.5.3 Safety

No changes in safety laboratory parameters, blood pressure (BP), heart rate (HR), or body temperature in any subject at any session in any study were of clinical concern. After IV administration, pain and erythema at the infusion site were the most frequently reported findings. The oral administration of lefamulin was generally well tolerated; infrequent mild and reversible gastrointestinal findings (nausea, abdominal pain and diarrhea) were reported. There were no systemic AEs of clinical concern and no drug-related SAEs in any study conducted to date. None of the subjects met withdrawal criteria. The stopping criteria were not reached in any of the studies.

In the Phase 2 study in subjects with ABSSSI, lefamulin (100 mg and 150 mg) administered intravenously over 5 to 14 days was safe and well tolerated. The incidence of treatment-emergent adverse events (TEAEs) considered related to study drug was numerically lower for subjects treated with lefamulin (34% and 39% in the 100 and 150 mg groups, respectively) than for subjects treated with vancomycin (53%). The types of TEAEs were consistent with a subject population under treatment for ABSSSI. The most frequently reported treatment-related TEAEs in subjects receiving lefamulin were headache, nausea, and diarrhea. Phlebitis at the infusion site was reported in 4 subjects in the lefamulin 100 mg group and 2 subjects in the 150 mg group. There was no increased incidence of phlebitis with increased dose. The most frequently reported treatment-related TEAEs for the vancomycin group were headache, nausea, pruritus, generalized pruritus, and diarrhea. All other related TEAEs were reported by 3 or fewer subjects in each treatment group.

In the Phase 2 study, study drug was discontinued due to an AE for 6 subjects (8 events). These AEs were hyperhidrosis, vomiting, headache, respiratory failure (an SAE), cellulitis, infusion site pain, and dyspnea in the lefamulin groups; and drug eruption in the vancomycin group. Six of these 8 events were considered related to study drug (hyperhidrosis, vomiting, headache, infusion site pain, and dyspnea in the lefamulin groups and drug eruption in the vancomycin group). Five subjects experienced an SAE; none was considered related to study drug. These SAEs were abscess, respiratory failure, and cellulitis in the lefamulin groups; and accidental overdose (narcotics) and convulsion in the vancomycin group (Prince et al., 2013).

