### 2.2 Secondary Objectives

- Evaluate the Early Clinical Response in the Microbiological Intent-to-Treat (microITT) Analysis Set.
- Evaluate the Early Clinical Response PLUS improvement in vital signs in the ITT Analysis Set.
- Evaluate the Investigator's Assessment of Clinical Response at TOC in the microITT and Microbiologically Evaluable at TOC (ME-TOC) Analysis Sets.
- Evaluate the By-Pathogen Microbiologic Response at TOC in the microITT and ME-TOC Analysis Sets.
- Evaluate the safety and tolerability of lefamulin versus comparator in the Safety Analysis Set.
- Evaluate 28 day all-cause mortality in the ITT Analysis Set.

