Each AE or SAE reported will be assessed for intensity and the date and time of onset (if available), time relationship to dosing, duration, and outcome of each event will be noted.

Laboratory abnormalities are not considered AEs unless they are associated with clinical signs and symptoms or require medical intervention. Clinically significant abnormal clinical laboratory findings or other abnormal assessments that are associated with the disease being studied, unless judged by the Investigator as more severe than expected for the subject's condition, or that are present or detected at the start of the study and do not worsen, will not be reported as AEs or SAEs.

The Investigator will exercise medical and scientific judgment in deciding whether an abnormal clinical laboratory finding or other abnormal assessment is clinically significant.

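### Section 7.4 takes four pneumonia symptoms out of AE reporting with seriousness as the only written exception; this conflicts with Section 7 and leaves non-serious drug-related dyspnea unreliably captured

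*Protocol*

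**What the plan says.** Section 7.4 covers "clinical signs and symptoms of pneumonia which are assessed daily per protocol (i.e., dyspnea, cough, sputum production, and chest pain") and states that these "will not be reported as adverse events unless they meet the definition of a serious adverse event". The list is closed, introduced by i.e., and seriousness is the only exception written into it.

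Section 7 gives the general rules:
- Anything new or worse since consent is to be reported as an AE or SAE, whether or not it is thought drug-related.
- A diagnosis is preferred to its component symptoms, but a symptom that belongs to no diagnosis is recorded as an AE of its own.
- Clinical failure need not be recorded as an AE unless it is serious.
- Disease-related abnormal laboratory findings and other assessments are left out "unless judged by the Investigator as more severe than expected for the subject's condition".

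The safety comparison is a secondary objective in Section 2.2: "Evaluate the safety and tolerability of lefamulin versus comparator in the Safety Analysis Set". Section 9.7 builds it from AEs, laboratory tests, ECGs and vital signs, with AEs tabulated by severity and relationship and a table or listing of AEs leading to discontinuation of study drug.

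On the Phase 2 skin-infection study, Section 1.5.3 says "study drug was discontinued due to an AE for 6 subjects (8 events"). Dyspnea on lefamulin is among these events and among those judged related: "Six of these 8 events were considered related to study drug (hyperhidrosis, vomiting, headache, infusion site pain, and dyspnea in the lefamulin groups".

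**The concern.** Not recording ordinary pneumonia symptoms as AEs in a pneumonia trial is sensible. The difficulty is that Section 7.4 identifies the excluded events by naming four symptoms and gives sites no instruction for one of them that the investigator believes has another cause, or that is out of proportion to the pneumonia. Section 7 points one way for such an event and the literal list in Section 7.4 points the other. A site is likely to follow the specific rule that names the symptom.

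At stake is consistent recording across about 125 centers, and whether a non-serious drug-related dyspnea reaches the safety tables. Section 1.5.3 shows that dyspnea has already been attributed to lefamulin once.

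**Working it through.** **1. One event under each rule.** Take a non-serious dyspnea that is new or worse on treatment and that the investigator attributes to study drug.
- Section 7, general rule: an AE, because it is new or worse and relatedness does not matter.
- Section 7.4, read by its list: not an AE, because dyspnea is named and the event is not serious.
- Section 7.4, read by its subject (symptoms of pneumonia): outside the exclusion, so an AE.

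The protocol does not say which reading of Section 7.4 governs. Nor does Section 7.4 repeat the exception for findings worse than expected, so a CABP symptom of that kind is excluded under either reading.

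**2. Phase 2 counts (Section 1.5.3).**
- Events leading to discontinuation on lefamulin: hyperhidrosis, vomiting, headache, respiratory failure, cellulitis, infusion site pain, dyspnea = 7. On vancomycin: drug eruption = 1. Total 7 + 1 = 8, as stated.
- Judged related: 5 on lefamulin + 1 on vancomycin = 6, as stated ("Six of these 8 events were considered related to study drug").
- Eight terms for eight events means one dyspnea event. It is absent from the listed lefamulin SAEs (abscess, respiratory failure, cellulitis), and no SAE was judged related, so it was non-serious.
- Eight events fell in six subjects, so at least one subject had more than one. The text does not say whether dyspnea alone caused the stop.

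**3. Illustrative size.** Inputs: 1 event; 141 lefamulin subjects in Phase 2 (Section 1.5); 275 planned on lefamulin (Section 9.2). Assumption: the skin-infection rate carries over to CABP.
- Rate p = 1/141 = 0.71%.
- Exact (Clopper-Pearson) 95% limits: lower 1 − 0.975^(1/141) = 0.018%; upper, the 97.5% point of Beta(2, 140), = 3.89%.
- Expected events = 275 × p = 275 × 0.00709 = 1.95; at the limits, 0.05 and 10.7.
- Chance of at least one = 1 − (1 − p)^275 = 86%; at the limits, 5% and above 99.9%.
- With 313 lefamulin subjects (the 626 ceiling), the expected count is 2.2 (0.06 to 12.2).

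On the literal reading, none of these events, if non-serious, would be entered as an AE.

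**4. Whether the symptom scores fill the gap.**
- Section 6.10 and Table 8 grade intensity from absent to severe. No causality assessment is described.
- Scores are daily on study drug and then at EOT, TOC and LFU. They are not obtained at TOC or LFU after an IACR of Failure (Section 6.10; Table 3, note k). A subject whose drug is stopped for an AE and who starts other antibacterials for the CABP is an IACR Failure (Section 6.11.1), so later scores are lost for some of the subjects who matter here.
- Section 9.7 does not list the scores among the safety summaries. An analysis plan could add them, but it could not supply an attribution that was never collected.

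**The case against.** The strongest reply is that Section 7.4 is headed and worded as being about the disease under study. A dyspnea attributed to the drug is not a symptom of pneumonia, so Section 7 already makes it reportable. Table 8 supports this by tying chest pain to CABP and dyspnea to the pre-CABP state. A drug reaction with a diagnosis is reported under that diagnosis. Severity is graded in both arms, and a one-level worsening of any symptom at the early assessment makes the subject a non-responder, so an excess on lefamulin at that time would count against it in the FDA primary endpoint.

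Much of this stands, and it rules out several stronger conclusions that a reader might draw:
- That Section 7.4 bars these symptoms whatever their cause. This is the literal reading of the list but not the only one; the defect is that the conflict is left unresolved.
- That the trial cannot detect drug-related dyspnea. Severity is recorded, and diagnosed reactions are reported. What is missing is reliable capture as an attributed AE.
- That QT prolongation makes the chest pain exclusion a cardiac safety gap. The protocol does not link the two. QT is followed directly by triplicate ECGs, core-laboratory evaluation and QTcF stopping criteria, and clinically significant ECG findings are recorded as AEs.
- That such stops would be filed as lack of efficacy. Section 6.17.1 defines that reason by a need for other antibacterials and lists adverse event separately.

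The reply does not settle how sites should act. It depends on each investigator inferring a limit that Section 7.4 does not state, and it does not supply the missing exception for symptoms worse than expected.

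**Conclusion.** The point holds as an unreconciled conflict between Section 7.4 and Section 7, together with a missing exception for symptoms more severe than expected. A non-serious dyspnea judged drug-related would not reliably reach the treatment-emergent, relatedness or AE-discontinuation summaries, and the symptom scores do not replace them.

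The evidence on size is thin: one related dyspnea event among 141 subjects with skin infection. The figure of about 2 events in 275 (0.05 to 10.7) assumes that this rate carries over to pneumonia and should be read only as an illustration. The protocol offers no comparable evidence for cough, sputum production or chest pain. No efficacy, power or sample-size figure is affected. This is a worthwhile, inexpensive improvement to safety recording, not a flaw that undermines the trial.

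**What to change.** Amend Section 7.4 and the eCRF guidance to say:
- The exclusion applies only to dyspnea, cough, sputum production or chest pain that the investigator attributes to the current CABP and that is no more severe than expected for it.
- Any of these symptoms attributed to study drug or to another cause is recorded as an AE, including when it leads to stopping study drug.
- Symptoms that represent clinical failure of CABP treatment stay under the existing Section 7 rule (not an AE unless serious).

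Discontinuation alone should not trigger an AE record. At the assumed 79% ECR rate, about 275 × 0.21 = 58 subjects per arm would be non-responders. Those whose drug was stopped for worsening pneumonia would then enter the AE-discontinuation summaries, contrary to the clinical-failure rule.

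The cost is a short wording change, a small number of extra AE entries and some attribution judgement by investigators. No visit or procedure is added.

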## **7.5 Other Reportable Events**

Certain events that occur should be reported to the Sponsor as Other Reportable Events. These include the following:

- Potential Hy's Law (PHL)
  - The investigator is responsible for prompt reporting of any patient who has had both (1) AST or ALT > 3 x ULN **and** (2) total bilirubin > 2 x ULN at any point in the study (i.e., meets criteria for Potential Hy's Law). The investigator must complete the Hy's Law eCRF. Liver laboratory results should be followed locally every several days until resolution or stabilization of the laboratory abnormalities and reported using an unscheduled laboratory eCRF. If subsequent to the initial report of PHL, the investigator determines that the case meets serious criteria, it should be reported as an SAE using standard reporting procedures.
- Pregnancy exposure (subject becomes pregnant while taking study drug)

- Subjects who are pregnant at Screening are not permitted to take part in this study, however, Nabriva Therapeutics AG or their representative must be notified of any subjects that become pregnant while participating in this study (or the partner of a male subject). Although pregnancy is not technically an AE, all pregnancies must be followed to conclusion to determine their outcome. This information is important for both drug safety and public health concerns. It is the responsibility of the Investigator or designee to report any pregnancy in a subject that occurs during this study to Nabriva Therapeutics AG or their representative.
- Lactation exposure (subject was taking study drug while nursing an infant)
- Accidental exposure (someone other than the study subject was exposed to study drug)
- Overdose (subject received more than the prescribed dose of study drug within a given timeframe)
- Other medication errors that potentially place subjects at a greater risk of harm than was previously known or recognized (e.g., study drug was administered by an incorrect route).

## 8 DRUG SUPPLIES

### 8.1 Lefamulin (BC-3781)

The active substance being investigated in this study is lefamulin (BC-3781), present in the drug product as the acetate salt (BC-3781.Ac). Physicochemical properties can be found in the Lefamulin Investigator's Brochure.

#### Lefamulin IV Formulation

The drug product for IV administration is supplied by the Sponsor in 15 mL sterile concentrate vials as a concentrate of 150 mg of lefamulin in 15 mL of 0.9% saline (Ph. Eur./USP/JP) for dilution into 250 mL 0.9% saline buffered with 10 mM citrate to pH 5. The citrate buffered saline bags (PVC-free, latex-free) are also supplied by the Sponsor. Each concentrate vial has a minimum extractable volume of 15 mL. A description of the unit formula of the concentrate vial is provided in the Lefamulin Investigator's Brochure.

#### Lefamulin Oral Formulation

Oral lefamulin is supplied by the Sponsor as 600 mg yellow oval film coated immediate-release tablets. Details of the composition are **provided** in the Lefamulin Investigator's Brochure.

### 8.2 Moxifloxacin

#### Moxifloxacin IV Formulation

Moxifloxacin will be supplied by the Sponsor in ready-to-use 250 mL latex-free flexibags as a sterile, preservative free, 0.8% sodium chloride aqueous solution of moxifloxacin hydrochloride (containing 400 mg moxifloxacin) with pH ranging from 4.1 to 4.6. Moxifloxacin is presented as a yellow intravenous solution.

### Moxifloxacin Oral Formulation

The oral dose of moxifloxacin is provided by the Sponsor as an over-encapsulated film coated tablet containing 400 mg as hydrochloride.

Additional details regarding moxifloxacin are found in the product monograph.

## **8.3 Linezolid**

### Linezolid IV Formulation

Linezolid IV injection is provided by the Sponsor as a single-use, ready-to-use flexible plastic (latex-free) infusion bag containing 600 mg in 300 mL aqueous sodium citrate / dextrose solution.

### Linezolid Oral Formulation

The oral formulation of linezolid 600 mg is supplied by the Sponsor as an over-capsulated film-coated tablet.

Additional details regarding linezolid are found in the product monograph.

